11.6.3. Safety**Laboratory Parameters**

- If a laboratory value which is expected to have a numeric value for summary purposes, has a non-detectable level reported in the database, where the numeric value is missing, but typically a character value starting with '<x' or '>x' (or indicated as less than x or greater than x in the comment field) is present, the number of significant digits in the observed values will be used to determine how much to add or subtract in order to impute the corresponding numeric value.
 - Example 1: 2 Significant Digits = '< x' becomes $x - 0.01$
 - Example 2: 1 Significant Digit = '> x' becomes $x + 0.1$
 - Example 3: 0 Significant Digits = '< x' becomes $x - 1$
- If a laboratory value which is expected to have a numeric value for summary purposes, has a non-detectable level reported in the database, where the numeric value is missing, but typically a character value starting with ' $\leq x$ ' or ' $\geq x$ ' is present, then the corresponding numeric value will be set equal to x.
- The following will be used to convert laboratory values from SI units to conventional unit:
 - Phosphate: Divide the mmol/L value by 0.32290 to get the mg/dL value
 - Albumin: Divide the g/L value by 10 to get the g/dL value
 - Calcium corrected: Divide the mmol/L value by 0.2495 to get the mg/dL value
 - Hematocrit: Divid the Fraction of 1 by 0.01 to get the %

11.7. Appendix 7: Premature Withdrawals & Handling of Missing Data

11.7.1. Premature Withdrawals

Element	Reporting Detail
General	
 • Subject study completion (as specified in the protocol Section 5.8) was defined as completing all phases of the study including the follow-up visit, with the following exception: subjects who die while on study are also considered as having completed the study. The number of subjects who completed the study for purpose of the disposition table will consist of all randomized subjects who, as documented in the eCRF, have completed all study visits, including the follow-up visit. • Withdrawn subjects will not be replaced in the study. • All available data from subjects who were withdrawn from the study will be listed and all available planned data will be included in summary tables and figures, unless otherwise specified.

11.7.2. Handling of Missing Data

Element	Reporting Detail
General	
 • Missing data occurs when any requested data is not provided, leading to blank fields on the collection instrument : 
 ○ These data will be indicated by the use of a “blank” in subject listing displays. Unless all data for a specific visit are missing in which case the data is excluded from the table. ○ Answers such as “Not applicable” and “Not evaluable” are not considered to be missing data and should be displayed as such.
Outliers	
 • Any subjects excluded from the summaries and/or statistical analyses will be documented along with the reason for exclusion in the clinical study report.

11.7.2.1. Handling of Missing Hgb and Other Data

Element	Reporting Detail
Hgb	
 • The Hgb concentration analyzed by Quest Diagnostics is referred to as Hgb throughout this document. These data will be summarized and analyzed. If the Hgb concentration measurement is missing and a corresponding valid HemoCue Hgb concentration measurement is available, the HemoCue Hgb concentration measurement will be used for all summaries and analyses. • The dose response dataset will be based on the ITT population using an observed case dataset, comprising all non-missing data collected up to Day 29. For subjects who have a Day 15 Hgb measurement but a missing Day 29 Hgb measurement, a change from baseline at Day 29 value will be imputed using $2 * (\text{Day 15 Hgb} - \text{Baseline Hgb})$. The assumption is deemed appropriate based on phase 2a data indicating linear response over time. Any subject who prematurely

Element	Reporting Detail
	
discontinues dosing prior to Day 15 will be non-evaluable for the dose-response analysis. In general, the imputed data for the dose response analysis will not be used in summaries and figures, except for those generated specifically for dose response results. However, for descriptive summaries of Hgb over time, raw Day 29 Hgb will be summarised as well as Day 29 Hgb including imputations. The number of imputed Day 29 Hgb values will be summarized by treatment group.
 
• All other efficacy inference will be based on the ITT population using an observed case dataset.
Other Data	
• For laboratory data no imputation for missing data or premature discontinuation will be performed and the observed values will be used. The same approach applies to other assessments such as vital signs and electrocardiograms (ECGs) examination data.

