7.3. Efficacy

Hgb values to be used in the determination of the primary endpoint (Hgb change from baseline at Day 29) will be measured by the central laboratory as part of the Clinical Safety Laboratory Assessments (Section 7.4.6). Day 1 measurement will serve as the baseline value.

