8. SECONDARY STATISTICAL ANALYSES

8.1. Efficacy Analyses

8.1.1. Overview of Planned Efficacy Analyses

The secondary efficacy analyses will be based on the Intent-To-Treat population, unless otherwise specified. All secondary Hgb summaries/analyses will use the ITT population with an observed case on-therapy dataset. If the Hgb concentration measurement from Quest is missing and a corresponding valid Hemocue Hgb concentration measurement is available, the Hemocue Hgb concentration measurement will be used for all summaries and analyses.

Table 5 provides an overview of the planned efficacy analyses, with further details of data displays being presented in Appendix 14: List of Data Displays.

Table 5 Overview of Planned Efficacy Analyses

Endpoint	Absolute							Change or %Change from Baseline						
	Stats Analysis			Summar y		Individual		Stats Analysis			Summar y		Individual	
	T	F	L	T	F	F	L	T	F	L	T	F	F	L
Hemoglobin (Hgb)														
Summary of Treatment Difference for Hemoglobin (g/dL) Change from Baseline at Day 29 by Subgroups								Y	Y	Y				
Exploratory Summary of Repeated Measures Analysis for Hemoglobin (g/dL) Change from Baseline at Day 29								Y		Y				
Summary of Hemoglobin (g/dL) by Visit				Y	Y						Y	Y		
Summary of Hemoglobin (g/dL) Change from Baseline by Visit by Subgroups											Y			
Individual Subject Hemoglobin Change from Baseline at Day 29 with Means and 95% CIs												Y	Y	
Subjects Who Reach Pre-defined Hgb Stopping Criteria				Y			Y							Y

Endpoint	Absolute							Change or %Change from Baseline						
	Stats Analysis			Summar		Individual		Stats Analysis			Summar		Individual	
	T	F	L	T	F	F	L	T	F	L	T	F	F	L
Subjects Meeting Different Hemoglobin Criteria				Y							Y			
Subject Profiles of Hgb and Dose over Time						Y								
Hgb Assessments: Quest vs. HemoCue						Y								
Secondary Efficacy Endpoints														
Hepcidin				Y	Y						Y	Y		
CHr				Y	Y						Y	Y		
Hematocrit				Y	Y						Y	Y		
RBC Count				Y	Y						Y	Y		
Reticulocyte Count(%)				Y	Y						Y	Y		
Reticulocyte Count(Absolute)				Y	Y						Y	Y		
Plasma EPO				Y							Y			
VEGF				Y							Y			
Plasma EPO and Hepcidin						Y								
Individual Post-Dose EPO						Y								
Individual Post-Dose VEGF						Y								
Iron-related Parameters														
Ferritin				Y	Y						Y	Y		
Transferrin				Y	Y						Y	Y		
Transferrin Saturation				Y	Y						Y	Y		
Total Iron				Y	Y						Y	Y		
UIBC				Y							Y			
TIBC				Y	Y						Y	Y		

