11.3.2. Multiple Assessments

For assessments on or after Day 1, if after window assignment there are multiple valid assessments of a parameter from the central lab within the same window (nominal and slotted visit data), then the scheduled assessment at a nominal visit takes precedence over any unscheduled assessments and will be reported for summary statistics/analyses. If the scheduled assessment is missing for the target visit within the same window, then the last on-treatment value in the window will be reported for on-treatment summary statistics/analyses, and the last post-treatment value in the window will be reported for post-treatment summary statistics/analyses.

For assessments during the screening period prior to Day1, if after window assignment there are multiple valid assessments of a parameter from the central lab within the same window (nominal and slotted visit data), then the last/most recent values will be reported for summary statistics/analyses.

For the primary endpoint, Hemoglobin (Hgb), if the scheduled Hgb concentration measurement during the study (including screening, treatment, and follow-up period) from the central lab is missing and a corresponding valid HemoCue Hgb concentration measurement is available, then the HemoCue Hgb concentration measurement takes precedence over unscheduled Hgb concentration measurements within the same window and will be used for all summaries and analyses.

ECG values and vital signs measured at the local sites will be slotted and selected following the same algorithm applied to the central lab assessments described above and will be reported for summary statistics/analyses, unless otherwise specified.

All assessments, including local lab assessments, will still appear in the associated listings.

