9.	All Randomized	DM2	Listing of Demographic and Baseline Characteristics	The following demographic and baseline characteristics will be included in this listing: Year of birth, age, age category, sex, ethnicity, Geographic Ancestry, Rescreened, Child bearing potential, Diabetes,, Weight, Baseline Weight Category, Height, BMI, Type of ESA, Standardized Prior ESA dose, Standardized Prior ESA Category(actual eCRF value), Prior ESA (stratification factor from IVRS), Baseline Heart Rate, Baseline Diastolic Blood Pressure, Baseline Systolic Blood Pressure, Baseline Hgb, Baseline Hgb Category, Baseline Ferritin, Baseline Absolute Reticulocyte Count, Baseline Pre-dose Plasma Erythropoietin, Baseline iron-based phosphate binder (ferric citrate and sucroferric oxyhydroxide), Country.
10.	All Randomized	Listing 6.08	Listing of Race	Please make sure that the details shown on the template will be included in this listing.

ICH : Listings				
No.	Population	IDSL / TST ID / Example Shell	Title	Programming Notes
Medical Condition & Concomitant Medications				
11.	All Randomized	Listing 6.17	Listing of Concomitant Medications	This listing displays all data captured in the concomitant medications dataset, including medications used prior to screening and post-treatment.
Exposure				
12.	Safety	EX3	Listing of Exposure Data	
Efficacy				
13.	ITT	Listing 7.01	Listing of Hemoglobin Data	Hemocue Hgb is not used for calculation of "Change from Baseline". When scheduled Quest Hgb at Day 29 visit is missing, "Change from Baseline" can be calculated using imputed Hgb. Slotted post-treatment Hgb cannot be used for calculation of "Change from Baseline"
14.	ITT	Listing 7.01	Listing of Hemoglobin Data for Subjects Who Reach Pre-defined Hemoglobin Stopping Criteria	
Based on the HemoCue Hgb stopping criteria described in study protocol Section 5.6.2 Hemoglobin Stopping Criteria.
 
For programming purpose (1) compare Hemocue Hgb at a scheduled visit to Hemocue Hgb at previous scheduled visit (i.e. compare Day 15 back to Day 1, and Day 29 back to Day 15); (2) compare Hemocue Hgb at an unscheduled visit to that measured at previous scheduled/unscheduled visit within 2 weeks.
 
Remove the following columns from the template: (1) Imputed Day 29 Hgb (2) Change From Baseline

ICH : Listings				
No.	Population	IDSL / TST ID / Example Shell	Title	Programming Notes

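### A HemoCue reading that replaces a missing central-laboratory Day 29 Hgb is still compared with a Quest baseline, so any device offset enters the primary change; the order of HemoCue and imputation also needs stating once

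*SAP*

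**What the plan says.** **Source of the endpoint.** Protocol 7.3 says that Hgb for the primary endpoint "will be measured by the central laboratory as part of the Clinical Safety Laboratory Assessments". SAP 11.7.2.1 follows this: "The Hgb concentration analyzed by Quest Diagnostics is referred to as Hgb throughout this document".

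**Substitution.** The same SAP section says that when the Quest value is missing and a valid corresponding HemoCue value exists, "the HemoCue Hgb concentration measurement will be used for all summaries and analyses". SAP 8.1.1 repeats the rule for the secondary analyses. SAP 11.3.2 states it expressly for the primary endpoint, at screening, treatment and follow-up: if the scheduled central value is missing, "then the HemoCue Hgb concentration measurement takes precedence over unscheduled Hgb concentration measurements within the same window".

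**Baseline and change.** SAP 11.5.2.1 sets baseline as the mean of the Quest values at Week -2 and Day 1. SAP 11.5.2.2 defines change as the later value minus baseline, with no adjustment for device.

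**Imputation.** The next bullet of SAP 11.7.2.1 has this trigger: "For subjects who have a Day 15 Hgb measurement but a missing Day 29 Hgb measurement". The primary change is then set to twice the Day 15 change. SAP 7.1.2 uses the same trigger. Neither says that the Day 29 HemoCue value must be missing too.

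**Listing 13.** The programming note in SAP 11.14.12 says "Hemocue Hgb is not used for calculation of" change from baseline, and allows the imputed value when the scheduled Quest Day 29 result is missing.

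**The concern.** The primary endpoint is a within-subject difference. If both terms come from one device, a constant offset cancels. Under the substitution rule the Day 29 term can come from HemoCue while baseline comes from Quest, so the offset stays in the change. If the Quest Day 15 value is also missing, a HemoCue Day 15 reading can enter the imputation formula, which multiplies the offset by two.

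A second, smaller matter is that the derivation is not written the same way everywhere. SAP 3.2 gives the dose-response analyses to the sponsor and the remaining analyses to the contract research organisation. If one team follows the appendices and the other follows the Listing 13 note, a subject's listed change from baseline may differ from the value in the primary model.

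At stake are the affected subjects' responses in the Emax and linear models, and through them the target dose and the dose ratio.

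**Working it through.** The plan states no figure on this point, so there is none to reproduce. The check is a comparison of the rules, followed by a range for the size.

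**1. Device terms.** Let HemoCue read Quest plus d.

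| Case | Calculated change | Device error |
|---|---|---|
| Quest Day 29 present | Quest D29 − Quest baseline | 0 |
| Quest Day 29 missing, HemoCue present | (Quest D29 + d) − Quest baseline | d |
| No Day 29 value, Quest Day 15 present | 2 × (Quest D15 − Quest baseline) | 0 |
| No Day 29 value, Quest Day 15 missing, HemoCue Day 15 present | 2 × (Quest D15 + d − Quest baseline) | 2d |
| HemoCue Day 29 with HemoCue baseline (proposed) | (Quest D29 + d) − (Quest baseline + d) | 0 |

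The second and fourth rows assume that both baseline values are from Quest. If a baseline value is itself a substituted HemoCue reading, as SAP 11.3.2 permits, part or all of d cancels.

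**2. Inputs for the size.** About 15 evaluable subjects per arm (protocol 4.3) and an SD of 1 g/dL for Hgb change (protocol 9.2.1). The offset d is in neither document; 0.3 to 0.5 g/dL is an assumption. The number of affected subjects is not given either.

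**3. Arm mean, per affected subject.** Shift = d / 15:
- 0.3 / 15 = 0.020 g/dL
- 0.5 / 15 = 0.033 g/dL
- Standard error of an arm mean = 1 / √15 = 0.26 g/dL
- Ratio: 0.020 / 0.26 = 0.08 to 0.033 / 0.26 = 0.13, about a tenth of a standard error
- Doubled case: 0.04 to 0.067 g/dL

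**4. Linear slope, per affected subject in the 30 mg arm.** With 15 subjects at each of 0, 10, 15, 25 and 30 mg, the mean dose is 16 and the sum of squares is 15 × (256 + 36 + 1 + 81 + 196) = 8550. Shift = d × (30 − 16) / 8550:
- d = 0.3: 0.0005
- d = 0.5: 0.0008

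That is 1.0% to 1.6% of the slope of about 0.05 expected in protocol 9.2.1. Protocol Table 5 gives a precision of 0.018 for that slope (SDx 11, SDy 1).

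**5. If the Listing 13 note were followed instead.** A measured Day 29 value would give way to twice the Day 15 change. For illustration, take a baseline of 10.5, Day 15 of 10.0 and HemoCue Day 29 of 10.2 g/dL. The change is 10.2 − 10.5 = −0.3 by HemoCue and 2 × (10.0 − 10.5) = −1.0 by imputation. The size of such differences depends on the individual course. If the two fortnightly increments each have SD 0.7 (assumed) and correlation r, the imputation error has SD 0.7 × √(2(1 − r)). This is 0.99 g/dL at r = 0, 0.70 at r = 0.5 and zero at r = 1. It vanishes under exactly linear courses.

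**The case against.** A reader might infer that the SAP prescribes two conflicting primary values for the same subject. The documents do not support that.

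- SAP 8.1.1, 11.3.2 and 11.7.2.1 agree on substitution, and the ITT definition in SAP section 4 accepts Hgb from either source.
- In 11.7.2.1 substitution comes first and imputation second. The natural reading is that a substituted Day 29 value is no longer missing.
- The contrary text is one programming note to a listing. SAP 11.14.3 describes the shells as guidance only, the note permits the imputed value and does not require it, and the note to the primary table (Table 2.5) has no HemoCue exclusion.

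This stands, and it reduces the second matter to a wording gap.

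On the device offset, it can be said that protocol 5.1 calls HemoCue a validated device, that SAP Figure 2.4 plots Quest against HemoCue with regression lines, and that few subjects should attend Day 29 with a usable HemoCue reading and no central result. The plot would show an offset but corrects nothing. Small numbers limit the effect without removing it. Dropouts with no Day 29 HemoCue reading are imputed under either reading.

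On SAP Table 1, protocol 9.4 allows deviations to be explained in the analysis plan or the study report, and the substitution appears openly in three SAP sections. It is not hidden. But SAP 2.1 says that Table 1 sets out any changes from the protocol's analysis, and the table lists only the new baseline.

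**Conclusion.** The device point holds: the operative rule subtracts a Quest baseline from a HemoCue reading, and nothing in the plan removes the offset. The inconsistency also holds, as a listing note out of step with the appendices and an imputation trigger that omits the HemoCue condition. It does not amount to two rival primary analyses.

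The effect is small: about 0.02 to 0.03 g/dL in a 15-subject arm mean per affected subject, or about a tenth of its standard error. This rests on the assumed offset of 0.3 to 0.5 g/dL and the protocol's SD of 1 g/dL. A figure of about 1 g/dL for the imputation error should not be quoted without its assumption of independent increments with SD 0.7, and it arises only if the listing note overrides the appendices. The case for acting is that a primary value should be uniquely defined before unblinding, and that the correction is nearly free.

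**What to change.** State one order in SAP 7.1.2, 11.3.2, 11.7.2.1 and the Listing 13 note:

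1. Quest Day 29 minus the Quest baseline.
2. If Quest Day 29 is missing, HemoCue Day 29 minus a HemoCue baseline (mean of the Week -2 and Day 1 HemoCue readings).
3. Imputation only if both Day 29 values are missing, with the Day 15 and baseline values taken from the same device.

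Add a row to SAP Table 1 recording the HemoCue substitution as a departure from protocol 7.3.

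The cost is SAP wording and a short change to the derivation code. No new data are needed: the Time and Events table (protocol 7.1) already schedules HemoCue at Week -2, Day 1, Day 15 and Day 29.

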11.7.2.2. Handling of Missing/Partial Dates

Element	Reporting Detail
General	Partial dates will be displayed as captured in subject listing displays.
Adverse Events	
 • The eCRF allows for the possibility of partial dates (i.e., only month and year) to be recorded for AE start and end dates; that is, the day of the month may be missing. In such a case, the following conventions will be applied for calculating the time to onset and the duration of the event: 
 ○ Missing Start Day and Non-missing End Date: If the day in a start date is missing, e.g. - JUN2006, and the month is the one in which treatment started, assign the day to the day treatment started (i.e. the event is considered on-treatment as per Appendix 4, Section 11.4.2.2) if treatment start date <= AE end date). Otherwise, set to the first of the month, 01JUN2006. ○ Missing Stop Day and Non-missing Start Date: Last day of the month (28th, 29th, 30th, or 31st as appropriate for the month and year) will be used. If the last day of the month is after the stop date of study treatment in the same month and treatment stop date >= AE start date, then study treatment stop date will be used. ○ Missing Start Day and Missing End Day: If both the day in a start date and the day in an end date are missing, set them to the first day of the month and the last day of the month, respectively. • Completely missing start or end dates will remain missing, with no imputation applied. Consequently, time to onset and duration of such events will be missing. • The recorded partial date will be displayed in listings
Concomitant Medications	
 • Partial dates for any concomitant medications recorded in the CRF will be imputed using the following convention: 
 ○ If the partial date is a start date, a '01' will be used for the missing/unknown day and 'Jan' will be used for the missing/unknown month. ○ If the partial date is a stop date, last day of the month (28, 29, 30, 31, dependent on the month and year) will be used for the missing/unknown day and 'Dec' will be used for the missing/unknown month. • The recorded partial date will be displayed in listings.

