7.4.1.1. Time period and Frequency for collecting AE and SAE information

- Any SAEs assessed as related to study participation (e.g., protocol-mandated procedures, invasive tests, or change in existing therapy) or related to a GSK product will be recorded from the time a subject consents to participate in the study up to and including any follow-up contact.
- AEs will be collected from the start of Study Treatment (Day 1) until the Follow-up visit (see Section 7.4.1.4).
- Medical occurrences that begin prior to the start of study treatment but after obtaining informed consent may be recorded on the Medical History/Current Medical Conditions section of the eCRF.
- All SAEs will be recorded and reported to PPD within 24 hours, as indicated in Section 12.5.4.
- Investigators are not obligated to actively seek AEs or SAEs in former study subjects. However, if the investigator learns of any SAE, including a death, at any time after a subject has been discharged from the study, and he/she considers the event reasonably related to the study treatment or study participation, the investigator must promptly notify PPD.

NOTE: The method of recording, evaluating and assessing causality of AEs and SAEs plus procedures for completing and transmitting SAE reports to PPD are provided in Section 12.5.6.

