11.4.2.2. Treatment States for AE Data

For adverse events (AEs), treatment state will be defined as:

Treatment State	Definition
Pre-Treatment	AE Start Date < Study Treatment Start Date
On-Treatment	If AE onset date is on or after treatment start date & on or before treatment stop date +1. Study Treatment Start Date ≤ AE Start Date ≤ Study Treatment Stop Date + 1
Post-Treatment	If AE onset date is after the treatment stop date + 1. AE Start Date > Study Treatment Stop Date + 1
Onset Time Since 1 st Dose (Days)	If Treatment Start Date > AE Onset Date = AE Onset Date - Treatment Start Date If Treatment Start Date ≤ AE Onset Date = AE Onset Date - Treatment Start Date + 1 Missing otherwise.
Onset Time Since Last Dose (Days)	If Treatment Stop Date + 1 ≤ AE onset date: AE onset date – treatment stop date + 1 If Treatment Stop Date + 1 > AE onset date: AE onset date – treatment stop date Missing otherwise.
Duration (Days)	AE Resolution Date/AE End Date – AE Onset Date + 1

NOTES:

- If the study treatment stop date is missing then any AEs with a start date on or after study treatment start date will be considered to be On-Treatment.
- In the case of a completely missing AE start date, the event will be considered to have started on-treatment unless an end date for the AE is provided which is before start of investigational product; in such a case the AE is assigned as pre-treatment.

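### An AE with start and end day both missing, dated to the month of first dose, is imputed before treatment start and falls out of the on-therapy and post-therapy AE tables

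*SAP*

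**What the plan says.** SAP 11.7.2.2 notes that the eCRF lets the day of an AE start or end date be missing, and gives sub-rules:

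- **Start day missing, end date known.** If the month is the one in which treatment started, the instruction is to "assign the day to the day treatment started (i.e. the event is considered on-treatment as per Appendix 4, Section 11.4.2.2"), provided treatment start is not after the AE end date. Otherwise the 1st of the month is used.
- **Start and end day both missing.** The instruction is to "set them to the first day of the month and the last day of the month, respectively". The month of treatment start is not mentioned.

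SAP 11.4.2.2 then assigns treatment states. Pre-treatment is "AE Start Date < Study Treatment Start Date"; on-treatment is "Study Treatment Start Date ≤ AE Start Date ≤ Study Treatment Stop Date + 1". A note adds: "In the case of a completely missing AE start date, the event will be considered to have started on-treatment", unless a recorded end date precedes the start of investigational product.

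Protocol 7.4.1.1 sets the collection period: "AEs will be collected from the start of Study Treatment (Day 1) until the Follow-up visit". From consent, only SAEs related to study participation or to a GSK product are recorded. Other occurrences between consent and first dose may go to medical history.

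**The concern.** Three states of knowledge about the same event give inconsistent results. With a known end date on or after first dose, the event is on-treatment. With no start date at all, it is on-treatment by default. Only the intermediate case, where month and year are known but neither day is, yields pre-treatment. The SAP gives no reason for this.

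The result also disagrees with the protocol's collection rule. Leaving aside the related SAEs recorded from consent, an AE recorded for the month of first dose should have begun on or after that dose.

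Incidence and severity of AEs and SAEs is a stated secondary endpoint. No AE table is planned for pre-treatment events, so an event given that state has no table to move to. The error can only lower the on-therapy counts.

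**Working it through.** The plan states no figure to reproduce. The check applies its date rules to a case and then to the calendar.

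**1. Worked case (illustrative dates).** First dose is 15 June, last dose 13 July (Day 29), and the AE start month is June. Under SAP 11.4.2.2, onset is AE date minus treatment start if the AE is earlier, and that difference plus 1 otherwise. Duration is end minus start plus 1.

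| Recorded dates and rule | Imputed start | State | Onset | Duration |
|---|---|---|---|---|
| June to June, both days missing, as written | 1 June | pre-treatment | 1 − 15 = −14 | 30 − 1 + 1 = 30 days |
| June to 20 June, end date known, as written | 15 June | on-treatment | Day 1 | 20 − 15 + 1 = 6 days |
| June to June, both days missing, with the starting-month exception added | 15 June | on-treatment | Day 1 | 30 − 15 + 1 = 16 days |

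A June-to-July event with both days missing also starts on 1 June as written, although it plainly runs past the first dose.

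**2. First-dose dates that trigger it.** The imputed 1st precedes the first dose on every date except the 1st of a month: 365 − 12 = 353 of 365 dates (353/365 = 96.7%).

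**3. Onset days exposed.** Assume first doses spread evenly over a 365-day year and a full 29-day treatment. The on-treatment window, to stop date + 1, is then 30 days, giving 365 × 30 = 10,950 onset days. For a first dose on day d of a month with L days, L − d + 1 of these fall in the starting month. Summing over d = 2 to L gives L(L − 1)/2:

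- seven months of 31 days: 7 × 465 = 3,255
- four months of 30 days: 4 × 435 = 1,740
- one month of 28 days: 378

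The total is 5,373, and 5,373/10,950 = 49.1%. On-treatment events dated only to a following month are imputed to its 1st and stay on-treatment; in the example, 1 July is Day 17.

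**4. Displays affected.** Of AE Tables 3.1 to 3.20 in SAP 11.14.8, sixteen are titled on-therapy and three post-therapy (3.3, 3.5 and 3.13). That makes 19 of 20, including the tables for serious events and events of special interest. Listing 20, of on-therapy treatment-related AEs, would also omit the event. Table 3.1, the overview, has no such limit in its title. Figure 3.1 has none either, although Table 6 in SAP 8.2.1 marks an AE figure on the row for on-therapy common AEs, so it probably loses the event. Listing 18, of all AEs, keeps it.

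**The case against.** **The conventions may not be meant to set treatment state.** SAP 11.7.2.2 introduces them with a narrower purpose: "the following conventions will be applied for calculating the time to onset and the duration of the event". Treatment state appears only in the parenthesis of the first sub-rule. That justifies asking the SAP to be explicit, but it does not rescue the rule. The parenthesis ties imputation to 11.4.2.2, and no other rule gives a state to a partly missing start date. Even on the narrow reading, an AE collected from Day 1 would get a negative onset time.

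**Some pre-treatment labels would be right.** This stands. A related SAE recorded from consent can begin in the starting month before dosing.

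**The default for a completely missing start date covers a different case.** Also true: no event falls under both rules. The two are inconsistent in how cautious they are; they do not contradict each other for a single event.

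**The event stays visible and should be rare.** Several listings have no on-therapy limit (all AEs, fatal AEs, non-fatal SAEs, events of special interest), and the recorded partial date is displayed. AEs are assessed at Days 1, 15, 29 and 43, SAEs are reported within 24 hours, and data are cleaned before database freeze. This limits the likely number. It does not make the tabulated counts correct.

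**Conclusion.** The defect holds. The rule for two missing days lacks the exception given in the same section, and it turns AEs in the month of first dose into pre-treatment events unless dosing began on the 1st. For all but certain related SAEs that label is wrong, and it lowers on-therapy counts. It should be corrected before database freeze. The primary hemoglobin analysis is not affected.

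Three stronger readings are tempting, and the documents do not support them:

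- **That the event leaves every AE table.** The titles show 19 of 20. Table 3.1 is not shown to lose it, and the listing of all AEs keeps it.
- **That about 97% of such events are lost.** The 96.7% is a share of calendar dates for the first dose. On the even-spread assumption, about 49% of on-treatment onset days are exposed, and only for events with both days missing.
- **That a count can be given for the 90 planned subjects.** The documents give neither a rate of partial dates nor an AE count. The number is probably small.

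A single event can still show in arms of about 18. SAP 8.2.2.1 calls an AE common at 2 or more subjects in any group or at least 2% of all daprodustat subjects. With 4 × 18 = 72 daprodustat subjects (assuming all are dosed), 2/72 = 2.8% qualifies and 1/72 = 1.4% does not. Losing one of two reports would drop the term from the common-AE table.

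**What to change.** Replace the start-date part of the sub-rules in SAP 11.7.2.2 with one rule:

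> If the start day is missing and the month is the month of first dose, set the start to the treatment start date, whether the end date is known, partial or missing, unless the recorded end date or other recorded information (such as a pre-dose SAE report) shows that the event ended or began before first dose. Otherwise use the 1st of the month.

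Add a sentence saying that imputed dates determine treatment state under 11.4.2.2. The new rule also covers a missing start day with a completely missing end date, such as an ongoing AE, which no sub-rule addresses now.

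The cost is two sentences and a small programming change before unblinding. The one downside is that a related SAE that began before dosing in the starting month, with an unknown day and nothing recorded to show it was earlier, would count as on-treatment. That is the conservative direction.
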